### **Inclusion/Exclusion Criteria:**

#### **Inclusion Criteria**

- female
- 18 - 45 years of age
- Patient at HH, WAHS, UConn Health
- given birth < 48 hours to a singleton infant > 37 weeks gestational age
- having intention to BF
- provided standardized BF basics during their antenatal care
- with access to the internet via own smartphone, other device, or study-provided smartphone (provided at baseline and returned at 6-month research visit)
- willing/able to consent to participate
- having ability to read and write English as the intervention has not been tested in Spanish speaking population.
- assessed by a lactation consultant (CLC/IBCLC) during BF before discharge

#### **Exclusion Criteria**

- <18 or  $\geq 46$  years of age
- women with history of significant mental health disorder (e.g., major depression, schizophrenia, or bipolar disorder) due to additional challenges in the capacity for self-management
- neurological or skin condition that inhibits, diminishes, or otherwise prevents sensation, such as eczema, rash, dermatographism on non-dominant forearm
- delivery of an infant with medical complications or congenital anomalies
- inability to communicate in English – although approximately 23% of the Connecticut population is Hispanic/Latinx (see page 25), women who speak/write in Spanish and other languages beside English will be excluded because our intervention has not been tested in Spanish.

#### **Post Enrollment Exclusion Criteria**

Participants who are enrolled in the study may be withdrawn due to any of the following criteria:

- non-compliance with study procedures such as failing to log daily entries and completing data collection points. At each data collection point, participants will be reminded via text to complete the surveys, with pushes from REDCap as needed to encourage completion. If needed, participants are followed up with a phone call or email to complete the surveys. If they do not complete the survey, they will be contacted for the next data point. If they do not complete three consecutive data points, they will be removed from the study, however any data collected will be used in analysis.
- Participants will be removed from the study at their own request.

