1	Days 1-5	Intervention Group ONLY: BL: 1 entry/ day Texts 2 times/ week breastfeeding coaching with links to Breastfeeding Modules 1-3 Maternal/Infant Care Modules 1-2	Personal computer/ smartphone	5 mins per entry  10 mins/ module	
	Days 1-5	Control Group ONLY: Texts 2 times/ week with links to Maternal/Infant Care Modules 1-2	Personal computer/ smartphone	10 mins/ module	
	Day 5	Both Groups: BB, PIS, MWB Control Group only: BL	Personal computer/ smartphone	10 mins	\$25 UConn Greenphire Gift Card or ecard
2	Days 8-12	Intervention Group ONLY: BL: 1 entry/ day Texts 2 times/ week breastfeeding coaching with links to Breastfeeding Modules 4-6 Maternal/Infant Care Modules 3-4	Personal computer/ smartphone	5 mins per entry  10mins/ module	
	Days 8-12	Control Group ONLY: Texts 2 times/ week with links to Maternal/Infant Care Modules 3-4	Personal computer/ smartphone	10 mins/ module	
	Day 12	Both Groups: BB, PIS, MWB Control Group only: BL	Personal computer/ smartphone	10 mins	\$25 UConn Greenphire Gift Card or ecard
3	Days 15-19	Intervention Group ONLY: BL: 1 entry/ day	Personal computer/	5 mins per entry	

		Texts 2 times/ week breastfeeding coaching with links to Breastfeeding Modules 7-9 Maternal/Infant Care Modules 5-6	smartphone	10mins/ module	
	Days 15-19	Control Group ONLY: Texts 2 times/ week with links to Maternal/Infant Care Modules 5-6	Personal computer/ smartphone	10 mins/ module	
	Day 19	Both Groups: BB, PIS, MWB Control Group only: BL	Personal computer/ smartphone	10 mins	\$25 UConn Greenphire Gift Card or ecard
Weeks 4-6	Days 21-40	Intervention Group ONLY: BL: 1 entry/ day Texts 2 times/ week breastfeeding coaching with links to Maternal/Infant Care Modules 7-12	Personal computer/ smartphone	5 mins per entry 5 mins/ module	
	Days 21-40	Control Group ONLY: Texts 2 times/ week with links to Maternal/Infant Care Modules 7-12	Personal computer/ smartphone	5 mins per entry	
Week 4	Day 26	Both Groups Infant development and play modules at 4 weeks	Personal computer/ smartphone	10 mins	

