#### Self-Regulation Skills and Abilities.

**Index of Self-Regulation.** The Index of Self-Regulation is an NINR common data element used across several populations which assesses an individual's general behavior and change effort to make behavioral changes and modulate thoughts, emotions, and behaviors to achieve goals.

**Breastfeeding Algorithm.** An adaptation of the LATC scale, through texted UConn Health REDCap link women will assess daily (*BSM* intervention) or weekly (attention control) infant awake/sleep state, signs of hunger, number of attempts to latch, strength of latch and of suck, pattern of pauses and sucks, and time duration of BF sessions.

**Maternal Assessment of Infant BF Behaviors.** A clinical indicator of four infant BF behaviors based on the nursing personality assessment, maternal report, and digital recording of infant BF behaviors.

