**6) Potential risk for participant burden and inconvenience.** Based on our pilot study results, women reported the baseline data collection to be burdensome. We addressed this risk by removing several questionnaires to decrease participant burden and recruiting during the prenatal period. We anticipate by recruiting women during the prenatal period, women will be prepared for the time for participation and decrease the time burden. Women in the pilot study, reported that completing the paper BF diary 6 times a day was burdensome. For this project, we are using a text-based daily (one entry) BF diary. Women did not report the weekly measurements via UConn Health REDCap as burdensome and that the bi-weekly texting contact was supportive without burdening them to travel to face-to-face visits and places the mother-infant dyad at risk for illness, such as COVID-19. The initial data collection

appointment will take approximately 45-60 minutes. The daily breastfeeding log will take 5 minutes/1 times a day for the first three weeks and from 15 days to 6 weeks a weekly breastfeeding log for 5 minutes a day. The scheduled data collection at Weeks 1, 2, 3, 9, 12, and 18 will take 30 mins to complete. The scheduled data collection for Weeks 6 and 24 will take 60 minutes. Additionally, participants may find logging daily feeding behaviors and multiple questionnaires an inconvenience. Receiving regular texts about their breast-feeding status may also be inconvenient. However, there is evidence to show that support via email and text during the first few weeks of delivery can be beneficial to breast feeding behaviors.

**7) Potential risk for eye strain with prolonged period of time looking at the computer/text screen.** We will instruct participants to use a low light setting and the use of anti-glare software to reduce the strain. Participants will also receive reminders and daily surveys to complete, which may be inconvenient. The time commitment is explained in detail in the consent and will be verbally explained to each subject prior to signing the informed consent. Additionally, we will limit reminders to texts and text pushes via REDCap related to missing data and scheduling 6 week and 6-month research visits, with follow up phone calls as needed to encourage completion, or phone calls to address emergent clinical concerns to decrease the inconvenience to the participant.

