**8) Protection of risks related to BF and infant health outcomes.** Infants who BF or formula feed <6 times a day are at risk for dehydration and inadequate calorie intake. Women in the *BSM* intervention group will record daily number of feedings in their daily BF journal. Women in the attention control group will record the number of feedings per day once a week. A record of <6 feedings over a 24-hour period will trigger a notification email via UConn Health REDCap to the research team. The research nurse will contact the participant, evaluate the situation, and decide on the need for referral to a lactation specialist or their healthcare provider. This will also be done on a case-by-case basis. In our pilot study, no participants were referred for inadequate daily feedings. If the participant indicates they are having any difficulty such as mastitis or extreme pain, they will always be told to contact their PCP. Participants at every step of the research study will be encouraged to contact their provider if they are experiencing severe pain or discomfort such as fever.

**9) Protection of risks related to COVID-19 transmission.** Research team members will practice COVID-19 prevention measures at all points of face-to-face contact which include antenatal clinic, inpatient postpartum unit, follow-up data collection at 6 and 24 weeks at the Ambulatory Women's Health Services clinic, Hartford Hospital Lactation clinic, the School of Nursing BBL at UConn Health or UConn Health Outpatient Obstetrics/Gynecology Clinic. These measures will minimize personal density, allow distances, wear personal protective equipment and follow best practice consistent with CDC guidelines, state guidelines, and applicable University and hospital policies. In addition, the study design delivers standardized and best practice BF and BNP problem-solving skills during an acute period of pain when the rate of BF cessation is the highest via mobile technology and when face-to-face visits are most burdensome and places the mother-infant dyad at risk for illness, such as COVID-19.

**10) Protection of research team against biohazards.** All research teams will complete Biohazard and Transportation of Biohazard training through UConn Environmental Safety Department. Collection, or Hartford Hospital Health Stream, storage and assays of biohazardous samples will be performed in accordance with established safety guidelines and regulatory requirements.

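### Women may be withdrawn for not logging daily, a task only the BSM arm has, and in both arms outcome follow-up ends after three consecutive missed data points

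*Combined protocol and SAP*

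**What the plan says.** The Post Enrollment Exclusion Criteria open with a permissive statement: "Participants who are enrolled in the study may be withdrawn due to any of the following criteria". The first ground is "non-compliance with study procedures such as failing to log daily entries and completing data collection points". No number or duration of missed log entries is given. The section then describes reminders by text, REDCap push, phone or email, and ends with a firm rule: "If they do not complete three consecutive data points, they will be removed from the study, however any data collected will be used in analysis".

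The log differs by arm. Table 1 lists one entry a day under the intervention group only and gives controls the log on the assessment day. The Breastfeeding Algorithm paragraph agrees: "women will assess daily (*BSM* intervention) or weekly (attention control) infant awake/sleep state". So does item 8 of Protection against Risk: "Women in the attention control group will record the number of feedings per day once a week".

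The length of daily logging is not settled. For Days 21-40 (weeks 4-6), Table 1 gives the intervention group "BL: 1 entry/ day Texts 2 times/ week breastfeeding coaching with links to Maternal/Infant Care Modules 7-12". Item 6 of Protection against Risk, naming no arm, has the log daily "for the first three weeks and from 15 days to 6 weeks a weekly breastfeeding log for 5 minutes a day".

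On analysis, SA2 starts with chi-square tests of exclusive breastfeeding at 6, 9, 12, 18 and 24 weeks, followed by a logistic mixed model. Models use observed data, with multiple imputation under missing at random as the sensitivity analysis. Data Analysis and Management names no analysis population.

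**The concern.** There are two separate problems.

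First, the daily journal is part of the BSM treatment: Intervention Administration lists it under design fidelity. Withdrawing a woman for not keeping it is withdrawal for treatment non-adherence, and only BSM women can meet that ground. The BSM women left under observation may then differ from those randomised in a way that has no counterpart among controls.

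Second, the three-miss rule turns a run of missed surveys into permanent loss of outcome data in both arms. Missing the Day 5, 12 and 19 surveys is enough. Her week 1-3 pain data are already lost by then; the rule also gives up weeks 6 to 24, including every exclusive-breastfeeding endpoint. This works against the plan's own aim of minimising attrition.

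The direction of any bias is unknown. Non-loggers may be women whose breastfeeding is going badly, or women who simply find logging a burden, as pilot participants said of the paper journal (Preliminary Studies 1.2).

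**Working it through.** **The plan's own sample size.** Inputs from Justification of Sample Size: d = 0.39, two-sided alpha 0.05, 80% power, 25% loss. Per arm, n = 2(1.960 + 0.842)²/0.39² = 103.2, so 104; 104/0.75 = 138.7, so 139; total 278 against 280 stated. With 140 × 0.75 = 105 per arm, power is 0.807. The figure reproduces. The 25% allowance is not split by arm, so it protects power but not against differential loss.

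**Endpoints forgone under the three-miss rule.** Follow-up is at weeks 1, 2, 3, 6, 9, 12, 18 and 24.

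| Three misses end at week | Exclusive-breastfeeding time points never sought (of 5) |
|---|---|
| 3 | 5 |
| 6 | 4 |
| 9 | 3 |
| 12 | 2 |
| 18 | 1 |

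**Illustrative bias, exclusive breastfeeding at one time point.** All rates here are assumptions. Let p be the true proportion in both arms (no effect), q the proportion among removed women and w the share removed. The observed proportion is (p − wq)/(1 − w). With p = 0.50, q = 0.15 and removal of 6% in BSM (about 8 of 140) against 2% in control (about 3 of 140):

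- BSM: (0.50 − 0.009)/0.94 = 0.522
- Control: (0.50 − 0.003)/0.98 = 0.507
- Odds ratio: (0.522/0.478)/(0.507/0.493) = 1.06

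The false-positive rate is a two-sided normal approximation at nominal 5%, first with 140 per arm less removals only, then with a further equal 25% loss in both arms.

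| Removed, BSM v control | OR, q = 15% | OR range, q = 0 to 40% | OR, q = 65% | False-positive rate, q = 15% | Same, with 25% equal loss |
|---|---|---|---|---|---|
| 6% v 2% | 1.06 | 1.09 to 1.02 | 0.97 | 5.7% | 5.5% |
| 10% v 2% | 1.14 | 1.20 to 1.04 | 0.95 | 8.1% | 7.3% |
| 20% v 5% | 1.32 | 1.50 to 1.08 | 0.89 | 19% | 15.6% |

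Removal of 8% v 4%, which averages to the pilot's 6% attrition, gives 1.07 at q = 15%. At q = 50% the odds ratio is 1.00 in every row.

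**Illustrative bias, continuous outcomes such as pain.** Suppose a further share x of the BSM arm is withdrawn on top of 25% loss in both arms, and those women would have scored k SD worse than the BSM women who remain. The spurious benefit is (x/0.75) × k.

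- x = 10%, k = 0.25 to 1.0: 0.133 × k = 0.03 to 0.13 SD, or 9% to 34% of d = 0.39. False-positive rate 5.6% to 15.4%. Power with 91 v 105 women: 0.777.
- x = 20%, k = 0.25 to 1.0: 0.267 × k = 0.07 to 0.27 SD, or 17% to 68% of d. False-positive rate about 7% to 43%. Power with 77 v 105 women: 0.739.

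**The case against.** The strongest reply is that one phrase is being read in isolation. The bullet gives examples of non-compliance and then sets out how it is handled, with repeated reminders and removal after three consecutive missed data points. That is the only trigger with a threshold and the only mandatory one, and it is the same in both arms. No section describes removing anyone for missed logs alone. This reading is possible, but missed daily logging is still a listed ground, and the reading leaves the three-miss rule untouched.

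The log is also more than treatment. It contains the algorithm used to measure exclusivity and duration, and it feeds the low-feeding alert. That is correct, and it is a further reason not to end follow-up because of it.

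The size is also open to challenge. Every removal rate is assumed. The pilot's 6% attrition arose with a paper diary kept six times a day, now one text entry. At that scale the distortion is slight. The chi-square test is only a first step, and the mixed model uses data from before removal. No per-protocol exclusion is described. Nobody knows how many women would respond after three failed rounds of contact, and the plan limits contact on purpose: "we will limit reminders to texts and text pushes via REDCap related to missing data". All of this stands and keeps the point moderate. But retaining earlier data does not supply the later outcomes, and imputation under missing at random does not cover withdrawal that depends on outcomes nobody observed.

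**Conclusion.** The concern holds. The text permits withdrawal for non-adherence in the BSM arm alone, and it ends outcome collection in both arms after three consecutive misses, forgoing between one and all five exclusive-breastfeeding time points.

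The likely distortion is small if loss stays near the pilot's level: an odds ratio of about 1.06 to 1.07 under no effect, assuming 15% exclusive breastfeeding in removed women. It becomes material only if removal is much more frequent and unequal, for which the documents give no evidence. All the illustrated odds ratios lie below the planned 2.5. The direction is not known. The rule should still be changed, because the loss is avoidable and outcomes not sought at the time cannot be recovered at analysis.

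The conflict over how long and how often the log is kept is a lesser point, but it leaves the daily-logging ground without a fixed meaning.

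**What to change.** - Delete missed daily logging as a withdrawal ground and record it as adherence. Intervention Administration already has REDCap tracking journal completion, so no new system is needed.
- Replace removal after three missed points with continued scheduled surveys and invitations to the 6- and 24-week visits, in both arms, unless the woman withdraws consent.
- State in Data Analysis and Management that all women are analysed in the group to which they were randomised. Report withdrawals by arm and reason, and add a sensitivity analysis that departs from missing at random.
- Reconcile the log schedule in Table 1 with item 6 of Protection against Risk, naming the arm.

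The cost is a short amendment, some extra reminders (which the plan chose to limit), staff time for the two visits, and incentives. From Economic Considerations, a woman who misses weeks 1-3 and then resumes would receive at most $50 + 3 × $35 + $75 = $230, with no completion bonus. For 8 such women that is 8 × $230 = $1,840. The change helps only women whose follow-up is still open when it takes effect.

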## **Promoting Self-Management of Breast and Nipple Pain with Biomarkers and Technology (PROMPT) for Breastfeeding Women study (1 R01 NR020041-01) RCT**

### **Purpose/Introduction:**

Every year, 1 million women cease breastfeeding (BF) before 6 months, the minimum time required for optimal maternal well-being and to promote their infant's health, physical growth, and development. The highest rate of BF cessation occurs within 3 weeks after delivery, with 30% of women ceasing BF due to acute breast and nipple pain (BNP). BNP is a complex and understudied biobehavioral phenomenon involving nociceptive signaling that stimulates multiple pathways - somatic (mechanical compression and cracked nipples), visceral (uterine cramping), and the autonomic nervous system (engorgement). Enhanced pain sensitivity, a physiologic pro-nociceptive state measured by somatosensory function and genomics, may increase women's sensitivity to BNP. Women who experience BNP beyond BF initiation report lower BF self-efficacy a key predictor of BF at 6 months, and increased symptoms of maternal distress (anxiety, depression, stress, and fatigue), which contribute to a greater risk of early BF cessation (< 3 weeks BF), decreased maternal well-being, and low maternal self-efficacy to care for their infant. Thus, a critical gap exists in identifying effective biobehavioral self-management interventions for women during BF initiation to manage BNP, increase BF self-efficacy, BF duration and decrease symptoms of maternal distress.

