**The rationale for the timing of data collection at baseline, 1, 2, 3, 6, 9, 12, 18, and 24 weeks.** In the proposed RCT, the *BSM* intervention will begin the first week after birth, when women shelter at home to BF, and have access to a smart phone, thus providing women with standardized and best practice BF and BNP problem-solving skills during an acute period of pain when the rate of BF cessation is the highest. In our pilot study, we found statistically significant and clinically meaningful differences in *pain intensity* at 1 and 2 weeks and *pain interference* as predictive of BF self-efficacy at 6 weeks between groups, especially among women with increased pain sensitivity at baseline. Thus, the second and third weeks are an important period for assessing the length of time needed for the *BSM* intervention to support the women's use of knowledge and skills for BNP self-management and its impact on proximal and distal outcomes. The 6, 9-, 12-, 18-, and 24-weeks data points will allow us to extend our study, explore the effect of the intervention on maternal well-being, and DNA methylation of pain sensitivity SNPs on decreased BNP and BF exclusivity. All of the data points (baseline, 1, 2, 3, 6, 9, 12, 18, and 24 weeks) align with the national BF duration metrics and the duration of BF recommended by clinical agencies (WHO, CDC, ACOG, AAP, AWHONN). These nine data points will allow us to describe the impact of the *BSM* intervention on women's BNP intensity and interference, the risk of early BF cessation, the occurrence of BNP after BF initiation and the risk profile of acute to chronic pain.

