## 1. Preliminary Studies

[figure not shown]
**1.1. Recruitment and retention of women initiating BF.** [name] has conducted biobehavioral studies of BF using multiple methods. [name] adjusted the number of women approached to fulfill the planned enrollment based on infant gestation and study burden. For telephone and the text-based study designs, a **10 – 20% increase of the planned enrollment** met the sample size with a 90% retention of participants at 4 weeks with peak attrition at 2 weeks. Videotaping preterm and full-term infants BF and testing a BF diagnostic device prototype in the home required a **100% increase** of the planned enrollment with an 80 – 85% retention of participants at 4 weeks and peak attrition after 1 week. The pilot RCT used text communication, email, telephone contact and increasing monetary incentives to retain 94% of participants with peak attrition in 1 week.

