**5) Protection against risk of symptoms of maternal well-being distress.** All participants will receive a pamphlet for the Hartford Hospital affiliated Institute of Living Peripartum Mood Disorder group, Postpartum Support International and suicide hotlines in their hospital discharge packet. Research team members at baseline will be trained to identify participants who exhibit emotional distress and will contact the PI for further questioning and consideration of referral to a mental health professional or social worker before hospital discharge if necessary. Secondly, the research team will check weekly for the Edinburgh Postnatal Depression Scale scores. A score  $>10$  will trigger a texted script to the participant to ask how they are doing, inform them of their concerning score, ask them if they need a referral or follow up with their health care provider. If the participant is unresponsive to text, the PI will follow up with a phone call and immediate referral, if required. If the participant's response includes thinking about suicide, it will trigger an immediate notification to [name], which includes reporting suicide risk to the health care provider (stated in the consent), assisting participant to immediate assessment at an urgent care or emergency department. In our pilot study, out of the 60 women one participant sought treatment for depressive symptoms. The pilot study found that all the women we contacted responded positively to the text and phone call follow-up and appreciated the support and referral for additional support. Likewise, this protocol surveillance addresses the needs of women during the fourth trimester and aligns with the CDC *Hear Her* campaign.

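### Removing women after three consecutive missed surveys, possible from day 19, makes weeks 6 to 24 permanently missing for women who did not withdraw consent

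*Combined protocol and SAP*

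**What the plan says.** The rule is in the combined protocol and SAP under Post Enrollment Exclusion Criteria: "If they do not complete three consecutive data points, they will be removed from the study, however any data collected will be used in analysis". The section opens in permissive terms: "Participants who are enrolled in the study may be withdrawn due to any of the following criteria". Removal at the woman's own request is a separate bullet. Before removal there are text reminders and REDCap pushes, and "If needed, participants are followed up with a phone call or email to complete the surveys".

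The Significance section lists the schedule: "All of the data points (baseline, 1, 2, 3, 6, 9, 12, 18, and 24 weeks". Table 1 puts the post-baseline surveys on days 5, 12, 19, 40, 61, 82, 122 and 166. At weeks 1 to 3 the survey-day entry reads "Both Groups: BB, PIS, MWB Control Group only: BL"; the maternal well-being battery (MWB) contains the Edinburgh depression scale.

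On timing of risk, the Introduction states: "The highest rate of BF cessation occurs within 3 weeks after delivery". Section 1.1 reports that the pilot used several contact methods and rising incentives to "retain 94% of participants with peak attrition in 1 week".

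Hypothesis H2A concerns exclusive breastfeeding at weeks 6, 9, 12, 18 and 24. The analysis section plans models on observed data, followed by multiple imputation as a sensitivity analysis under missing at random. It plans no analysis under missing not at random.

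**The concern.** A woman who misses three surveys has not withdrawn consent, and she may answer later or attend a clinic visit. Removing her turns a gap into permanent loss. Because early surveys are a week apart and later ones three to six weeks apart, the rule acts fastest when women are most likely to be stopping breastfeeding.

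If silence is partly a consequence of pain or of having stopped, the women removed differ from those retained on the outcomes under test. Keeping data already collected does not supply outcomes that were never sought. What is at stake is the credibility of the week 6 to 24 comparisons, above all exclusive breastfeeding, which has its own power statement.

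**Working it through.** **1. The plan's sample size.** Inputs from Justification of Sample Size: d = 0.39, two-sided alpha 0.05, power 80%, loss 25%. Per arm, n = 2(1.960 + 0.842)² / 0.39² = 103.2, so 104. Then 104 / 0.75 = 138.7, so 139 per arm and 278 in total. The t-test version gives 104.2, so 105, and 105 / 0.75 = 140 per arm. The stated 280 is reproduced.

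**2. When the rule can be met** (days from Table 1):

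| Weeks missed | Days | Span | Rule met | Later data points lost |
|---|---|---|---|---|
| 1, 2, 3 | 5, 12, 19 | 14 days | day 19 | 5 |
| 2, 3, 6 | 12, 19, 40 | 28 days | day 40 | 4 |
| 3, 6, 9 | 19, 40, 61 | 42 days | day 61 | 3 |
| 6, 9, 12 | 40, 61, 82 | 42 days | day 82 | 2 |
| 9, 12, 18 | 61, 82, 122 | 61 days | day 122 | 1 |

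These are survey due dates. No completion window is defined, so actual removal could come some days later. Conversely, the protocol counts baseline as a data point; if unfinished baseline questionnaires count as a miss, the rule could be met at day 12.

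**3. What removal at day 19 forfeits.** 166 − 19 = 147 days of follow-up; 5 of 8 post-baseline data points; 5 of 5 exclusive-breastfeeding assessments; 5 of 9 depression-scale time points; 2 of 3 sensory-testing and biosample visits.

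**4. What the retained data contribute.** A woman silent at weeks 1 to 3 has baseline data at most. In the SA1 models baseline is a covariate and the first outcome is week 1, so she supplies no outcome value. She is also absent from the chi-square tests at weeks 6 to 24. Any imputation for her rests on baseline information only.

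**5. Power by total loss** (d = 0.39):

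| Loss | Women per arm | Power |
|---|---|---|
| 6% | 132 | 0.89 |
| 25% | 105 | 0.81 |
| 30% | 98 | 0.78 |

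Power is covered up to the planned loss.

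**6. How bias could arise** (illustration; all rates assumed). Suppose the intervention has no effect, the true exclusive rate is 50% in both arms, and every removed woman is not exclusively breastfeeding. With removal of 20% of controls and 10% of the BSM arm, the observed rates are 0.50 / 0.80 = 62.5% and 0.50 / 0.90 = 55.6%. The odds ratio is (0.556 / 0.444) / (0.625 / 0.375) = 0.75 instead of 1. With 15% and 10% removed it is 0.88. At a true rate of 30% the two figures are 0.83 and 0.92. With equal removal of 10% it stays at 1.0, although both rates are overstated. If the arms were exchanged, the bias would favour the intervention.

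**7. How many women.** The documents give no removal rate. If 5 to 10% of 280 missed weeks 1 to 3 (14 to 28 women) and 30 to 50% of those would have responded later, about 4 to 14 women would lose outcomes because of the rule. Both ranges are assumptions. For scale, the pilot's 6% loss applied to 280 is about 17 women, and the planned 25% is 70.

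**The case against.** A reader might infer that the rule switches off depression and infant-feeding monitoring for women who fall silent when they are most at risk. The documents do not support that.

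- Both alerts under Protection against Risk need an entry by the woman. For depression, "the research team will check weekly for the Edinburgh Postnatal Depression Scale scores"; the feeding alert needs a recorded count. A fully silent woman produces neither from her first missed survey, so removal mainly ends reminder contacts. The exception is a BSM participant who skips surveys but still keeps the daily log or answers texts: for her, removal would close a working channel.
- The early weeks are documented as the period of highest breastfeeding cessation, not of highest depression risk.
- Alerts already raised have response pathways in items 5 and 8 of that section, and neither is said to depend on later surveys. All women also receive discharge information on support services.

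Three further objections have weight. Removal follows three failed rounds of reminders, and the section's opening makes withdrawal discretionary; but the bullet is mandatory, and that conflict itself needs correcting. The end of follow-up is inferred from the word for removal and from the absence of any later procedure; the plan does not spell it out, nor say whether the week 6 scheduler referral or the Epic flag would be cancelled. Lastly, the size is assumed: most of the 5 to 10% range exceeds the pilot's entire 6% loss. The illustration in step 6 also credits all missingness to the rule, when only women who would have responded later are attributable to it. The H1 contrasts at weeks 1 to 3 lose nothing through removal at day 19, because those surveys were already missed.

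**Conclusion.** The point holds as a matter of data retention and bias. The rule can remove a woman who has not withdrawn consent as early as the day-19 survey and, on its natural reading, forfeits every exclusive-breastfeeding outcome she could still have given. The planned analyses cannot correct loss that depends on unobserved outcomes.

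The size is unknown. The 4 to 14 women and the odds ratios of 0.75 to 0.92 show what could happen under stated assumptions; they do not estimate what will happen. Two larger conclusions should not be drawn: that the trial becomes underpowered, since the 25% allowance covers plausible loss, or that the rule dismantles safety monitoring. The change is still worth making, because the loss is avoidable and channels for later contact already exist: the scheduler referral for week 6, the appointment prompts at weeks 4, 18 and 20, and the Epic flag for both visits.

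**What to change.** In Post Enrollment Exclusion Criteria:

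1. Reconcile the permissive opening with the mandatory bullet.
2. Replace the removal sentence with wording such as: after three consecutive missed data points, survey reminders are reduced, but the woman remains enrolled and is contacted for later data points, at least for the week 6 and week 24 visits, unless she withdraws consent.
3. Cross-refer the rule to the existing depression-score and low-feeding pathways under Protection against Risk, so that the passages agree. No new clinical requirement is needed.

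The cost is protocol wording and some further unanswered contacts. Participant burden is a listed risk, so these contacts should stay within the reminder limits in that section, which already allow reminders about missing data and about scheduling the two research visits. Sample size and planned models are unchanged.
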